TITLE OF STUDY

Milk Desensitization and Induction of Tolerance in Children

Milk Allergy is a very common problem in children. Milk-induced symptoms effect up-to 20% of children, with detrimental effects on nutrition during critical periods of growth. Moreover, approximately 2-5% of children make IgE antibodies against cow's milk, which are responsible for severe allergic reactions and anaphylaxis. Milk is the second most common food causing life-threatening anaphylaxis in North America and Europe, and the most common food to cause life-threatening symptoms world-wide. Due to the ubiquitous nature of dairy products in our diet, milk is extremely difficult to avoid. Treatment of milk allergy is currently based on strict avoidance, and patients must carry injectable adrenalin (e.g. Epipen). Our study will assess a novel and potentially life-changing therapy, by actively treating milk allergy with Oral Immunotherapy. This may allow patients to **safely** consume dairy products. Treatment with oral-immunotherapy has been piloted in the USA and Europe, but there is no current research into milk-immunotherapy in Canada, depriving our population of a potential cure for this very common problem. We propose to perform a well-defined clinical study, using proper control groups and immunological measures to properly understand the ideal patients and the safest and most efficacious methodologies. If successful, this study will clearly increase the margin of safety for children and young adults who suffer from life-threatening milk allergy. It can also increase the consumption of dairy products within this population, providing nutritional benefits including improved bone mineralization and growth. We will also disseminate optimal milk- specific oral-immunotherapy protocols to practitioners for general use.

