1.13 Does oral immunotherapy (OIT) give patients the ability to normally ingest dairy products? In treating allergic conditions, we may achieve either temporary **desensitization**, or complete **tolerance**. Desensitization refers to a change in the amount of food antigen needed to cause allergic symptoms; it is a temporary state and is dependent on regular exposure to the substance in question, as is done for penicillin allergic patients who require drug desensitization. When the treatment with penicillin is ended, the patient loses the ability to safely ingest it within days to weeks, unless the therapy continues. In contrast, **tolerance** refers to long-term immunologic changes associated with the ability to ingest a food without symptoms and without ongoing therapy. Both scenarios are an improvement over the status quo; desensitization as therapeutic goal allows individuals more freedom from the risk of accidental ingestion in everyday settings; however, frequent if not daily exposure to the food would be required to maintain the desensitized state. Limited reports of three subjects suggested a loss of protection within 48h to weeks after elimination of the food from the diet (45-47). A more recent trial suggested that as long as participants ingested the maintenance dose of milk at least twice a week no allergic reactions were likely to occur(48). Achieving long-term clinical tolerance would allow safe food ingestion without ongoing therapy by inducing lasting immunologic changes; given the abundance of dairy products in our diet, it is crucial, to determine if we can achieve tolerance using our clinical protocol. We will utilize oral food challenges at the end of oral immunotherapy and one month following cessation of therapy to evaluate this question.

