3.3.3 Maintenance phase

Patients who reach the maintenance dose of 200 ml will be instructed to continue and consume 200 ml of milk daily for 1 month. They will then undergo an oral challenge (see above), with the maximum dose of 300ml.

If this 300 ml dose is tolerated, they will be permitted to consume dairy products without restrictions and attend regular follow up visits for 12 months. It will be recommended to consume dairy at least twice weekly, if not more, to maintain the desensitization.

Subjects who tolerate less than the 200 ml upper dose will be instructed to continue their maximum tolerated dose for the 12 month follow-up period, at which time another blinded milk challenge will be performed to determine if their tolerance increased.

3.3.4 Long Term Follow-up: to assess the persistence of milk desensitization from clinical, cellular and molecular perspectives, participants will be asked to return to the research center once a year for five years following the end of the Maintenance Phase. At these visits, participants will be asked about their dairy consumption, any reactions they may have experienced in the interval between the last visit and changes in their quality of life (as assessed by questionnaire). Participants will also have the following analyses done: SPT, salivary IgA, serum milk-specific IgE, IgA and IgG4 concentrations, Glycosylation state, Vitamin D levels, and B and T cell regulatory cell phenotyping. Participants will be reminded of the importance of continuing the consumption of dairy products in the maintenance of desensitization. Participants who have completed the study will be asked to reconsent to the extension. Given that these participants may not have scheduled visits to the hospital, to lessen their inconvenience, a delegated member of the study team might make a home visit in order to obtain informed consent

3.3.4 Control Subjects: Subjects randomized to no treatment will be followed every 3-6 months as is standard in our clinic for milk allergy. They will have skin testing and blood testing as on routine follow-ups, but they will be required to fill out symptoms diaries. At the end of the study period, oral desensitization will be offered to the control patients who had not spontaneously achieved tolerance.

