Appendix C Study Design

Visit 1: Explanation, Informed Consent, Skin testing, Basic Blood testing + Immune Tolerance Evaluation (CBC, biochem, specific IgE, IgG4, IgA, Treg, Breg)

Visit 2: Physical Exam, Blinded Placebo Controlled Food Challenge

Visit 3, 4: Physical exam, 2 Day in hospital Rush initiation of Oral Immunotherapy

Visit 5: Two weeks after rush initiation, Physical exam, symptoms diary, first dose escalation

Visit 6-21: (or more if necessary) Vital Signs, Symptom Diary, Escalation of Oral Immunotherapy

Visit 22, one week after completion: Physical Exam, Symptom Diary, Basic Blood testing + Immune Tolerance Evaluation (CBC, biochem, specific IgE, IgG4, IgA, Treg, Breg)

Visit 23, One month after completion of OIT escalation: Physical Exam, Symptom Diary, Basic Blood testing + Immune Tolerance Evaluation (CBC, biochem, specific IgE, IgG4, IgA, Treg, Breg)

Visit 24: One month after cessation of OIT: Physical Exam, Symptom Diary, Basic Blood testing + Immune Tolerance Evaluation (CBC, biochem, specific IgE, IgG4, IgA, Treg, Breg) Blinded Placebo Controlled Food Challenge

Visit 25: Three months after cessation of OIT: Physical Exam, Symptom Diary, Basic Blood testing + Immune Tolerance Evaluation (CBC, biochem, specific IgE, IgG4, IgA, Treg, Breg)

Visit 26: 6 Months after completion of OIT: Physical Exam, Symptom Diary, Basic Blood testing + Immune Tolerance Evaluation (CBC, biochem, specific IgE, IgG4, IgA, Treg, Breg)

Visit 27: 9 Months after completion of OIT: Physical Exam, Symptom Diary, Basic Blood testing + Immune Tolerance Evaluation (CBC, biochem, specific IgE, IgG4, IgA, Treg, Breg)

Visit 28: 12 Months after completion of OIT: Physical Exam, Symptom Diary, Basic Blood testing + Immune Tolerance Evaluation (CBC, biochem, specific IgE, IgG4, IgA, Treg, Breg)

AVAILABLE FACILITIES AND EQUIPMENT

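### The tolerance question rests on a challenge one month after therapy stops, but no treatment section stops milk, so as written a Visit 24 pass could not separate tolerance from maintained desensitization

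*Combined protocol and SAP*

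**What the plan says.** The title is "Milk Desensitization and Induction of Tolerance in Children". Section 1.13 separates the two ideas. Of desensitization it says that "it is a temporary state and is dependent on regular exposure to the substance in question". Tolerance, by contrast, "refers to long-term immunologic changes associated with the ability to ingest a food without symptoms and without ongoing therapy". It calls it crucial to find out whether tolerance can be achieved, and sets the test: "We will utilize oral food challenges at the end of oral immunotherapy and one month following cessation of therapy to evaluate this question".

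Appendix C carries the test: "Visit 24: One month after cessation of OIT", with a blinded placebo-controlled challenge. Apart from the baseline challenge at Visit 2, this is the only food challenge that Appendix C lists.

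The sections that govern milk intake are these:

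- Section 3.3.3, children who pass the 300 ml challenge: "they will be permitted to consume dairy products without restrictions and attend regular follow up visits for 12 months". It adds: "It will be recommended to consume dairy at least twice weekly, if not more, to maintain the desensitization".
- Section 3.3.3, children who stay below 200 ml: they are told to keep taking their maximum tolerated dose for the 12-month follow-up.
- Appendix B: the last row is 200 ml of undiluted milk for weeks 17 to 52. Nothing follows it.
- Section 3.3.4 (Long Term Follow-up): participants are reminded to go on consuming dairy so that desensitization is maintained.
- Section 3.3.5 (Withdrawal from therapy): the only stop described in the treatment sections is withdrawal of an individual child.

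On timing, Appendix C dates Visits 24 and 25 from cessation of OIT and Visits 26 to 28 from its completion. Section 3.3.4 (Documentation) dates follow-up at 3, 6, 9 and 12 months from completion.

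**The concern.** A test of tolerance, as section 1.13 defines it, needs a period without therapy before the challenge. Section 1.13 and Appendix C name such a period, but no section that tells families or staff what to do about milk puts it into effect, and section 3.3.3 points the other way.

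Three things are at stake. The first is interpretation: a child who has kept eating dairy and passes at Visit 24 may be tolerant or may be desensitized. The second is consistency: recruitment is from three centres, and staff working from Appendix C could stop milk while staff working from section 3.3.3 would not, so the pooled Visit 24 results could mix two different quantities. The third is conduct: section 1.13 itself reports, from three subjects, loss of protection within 48 hours to weeks of elimination, yet no section describes how a stop would be carried out.

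**Working it through.** The plan gives no figure for tolerance, so there is none to reproduce. The check sets the sections side by side and then dates the visits.

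**1. What a pass would show under each set of instructions**

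| Instructions followed | Exposure before Visit 24 | Meaning of a pass |
|---|---|---|
| Section 3.3.3, Appendix B, long-term follow-up | Dairy recommended at least twice weekly, or dose continued | Compatible with tolerance and with maintained desensitization |
| Section 1.13, Appendix C Visit 24 | One month after therapy stops | Could bear on tolerance, but contradicts section 3.3.3 |

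The first row rests on the protocol's own account. Section 1.13 cites a trial suggesting that "as long as participants ingested the maintenance dose of milk at least twice a week no allergic reactions were likely to occur". The recommendation in section 3.3.3 has the same frequency, although it speaks of dairy rather than the maintenance dose. On that account a desensitized child who follows the advice is expected to pass, and so is a tolerant child, so a pass hardly shifts the odds between the two. A failure would count against tolerance. On continued dairy the challenge could therefore refute tolerance but not establish it.

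**2. Where Visits 24 to 26 fall**

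Inputs: Appendix B starts 200 ml at week 17, taken here as the end of escalation, and its last week is 52. Section 3.3.3 gives one month of 200 ml daily. Assumption: 1 month = 52/12 = 4.33 weeks.

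Visit 24 = cessation + 4.33; Visit 25 = cessation + 13.

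| Cessation taken as | Week | Visit 24 | Visit 25 |
|---|---|---|---|
| End of escalation | 17 | 17 + 4.33 = 21.3 | 17 + 13 = 30.0 |
| End of the month at 200 ml | 17 + 4.33 = 21.33 | 21.33 + 4.33 = 25.7 | 21.33 + 13 = 34.3 |
| End of Appendix B | 52 | 52 + 4.33 = 56.3 | 52 + 13 = 65.0 |

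- Under the first two readings, Visit 24 lies inside the weeks 17 to 52 row, where Appendix B lists 200 ml.
- Under the first reading, Visit 24 also coincides with Visit 23, which Appendix C places one month after escalation is completed (17 + 4.33 = 21.3).
- Under the third reading, Visit 24 falls after Appendix B ends. The table is then silent: it neither continues milk nor stops it.
- If cessation is week 52 and completion is the end of escalation, Visit 26 falls at 17 + 26 = week 43, before Visit 24 at week 56.3.

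Under none of these readings does a dosing section write down an interval without milk before the Visit 24 challenge.

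**3. Where tolerance appears in the analysis plan**

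The hypothesis (section 2.0) defines success as daily intake of dairy without symptoms. None of the four objectives (section 2.1) asks about tolerance off therapy. Section 3.3.6 makes desensitization at one year the primary outcome and lists no tolerance outcome, and section 4.0 describes no analysis of one.

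**The case against.** The strongest reply is that OIT and dairy intake are different things. Section 3.3.3 separates protocol dosing at 200 ml daily from later free consumption, so OIT could end while dairy continues. The 3, 6, 9 and 12 month visits in Appendix C match those in section 3.3.4 (Documentation), which suggests that cessation and completion are loose synonyms for one event. If so, Visits 24 and 25 do have an anchor, and the timing problem reduces to wording. This is a fair reading and may be the intended one. It does not rescue the tolerance test, because dairy would still be eaten before the challenge.

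A reader might infer that cessation never happens, or that no child in the OIT arm would have an off-treatment interval. The documents do not support that. Section 1.13 and Appendix C both name the interval, Appendix B is silent after week 52, and for children who pass 300 ml dairy is permitted and recommended rather than required. The text contradicts itself, and choosing one side would settle by assertion what the investigators have to settle.

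It can also be said that the protocol uses the word tolerance loosely elsewhere, for a reaction threshold (sections 3.2 and 3.3.3), so the title alone is weak evidence of a formal aim. That is true of the title. Section 1.13 is not loose: it defines the term and names the test.

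**Conclusion.** The point holds as an internal inconsistency that should be fixed. The plan states a question and a test for it, and if the treatment sections are followed the test cannot answer the question. The ambiguity applies to every child in the OIT arm who reaches Visit 24, out of 42 planned. The number who would in practice be off milk cannot be derived from the documents.

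Two stronger conclusions should not be drawn. A pass on continued dairy would not show that a child is desensitized and no more; it would leave the two states undistinguished. Nor is the main result of the trial undermined: the primary outcome, the hypothesis and the four objectives do not rely on an off-treatment challenge. What cannot be supported as written is a conclusion about tolerance.

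This rests on the protocol's own definitions and, for the visit dates only, on a month of 52/12 weeks and on week 17 as the end of escalation.

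**What to change.** The investigators should reconcile sections 1.13, 3.3.3 and 3.3.4 with Appendices B and C on whether and when OIT stops, and whether and when dairy intake stops. Visits 24 to 28 should be tied to one defined date, with one term for it throughout.

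Then one of two courses follows:

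- If an off-treatment challenge is kept, list it in section 3.3.6 as a secondary outcome, with all children randomised to OIT in the denominator, and make the treatment sections agree with it.
- If it is not kept, confine the title, section 1.13 and the trial's conclusions to desensitization. The hypothesis needs no change.

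The second course costs only wording, but gives up the tolerance claim. The first may need more than wording, since the conduct of the off-treatment period would have to be written down. Which course to take, and any rule on milk intake, is for the investigators; no regimen is proposed here.

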3.0 Research Methods

3.1 Subject Selection: Eighty four boys and girls, between 6 to 20 years of age, diagnosed with IgE-mediated milk allergy, will be recruited for the study. Participants will be recruited from the allergy clinic at the Montreal Children's Hospital, Hopital Ste Justine, and the Centre de santé et de services sociaux de Chicoutimi.

Inclusion criteria: Children 6 years and older who satisfy **all** the following criteria will be included:

a. A **history** suggestive of IgE-mediated allergy to milk. An IgE-mediated reaction to a specific food is defined as a minimum of 2 mild symptoms and/or 1 moderate and/or 1 severe symptom that began within 1-20 minutes after ingestion or contact. Mild IgE-mediated symptoms include: pruritus, urticaria, flushing, or rhinoconjunctivitis. Moderate symptoms include angioedema (of face or lips), throat tightness, gastrointestinal complaints (vomiting, cramping, pain and/or diarrhea), or airway involvement (cough, nasal blockage, mucous); severe symptoms include bronchospasm, wheezing, hypoxia, cyanosis, low blood pressure, or circulatory collapse (shock) (appendix A ,table 1) (61).

b. The presence of **at least one** of the following confirmatory tests:

- (a) Positive skin prick test to milk (weal diameter 3 mm larger than that of the normal saline control). The allergen used will be commercially available milk extracts (Omega Labs, Montreal, QC). Skin tests will traced in ink, tape transferred to paper and wheal diameter measured by computer assisted planometry.
- (b) Detection of serum specific IgE (>0.35 kU/L) to milk or any of its proteins, measured by fluorescence enzyme immunoassay (Immunocap, Phadia, Uppsala, Sweden). The range for Immuncap is 0.35 – 100 and changes over time can be monitored effectively.

Following explanation of all facets of the protocol, informed consent and assent forms will be signed by the parents or legal guardian and subject, if applicable (Appendix B).

Exclusion criteria.

1. Patients with uncontrolled asthma or other uncontrolled respiratory diseases .
2. Malignancies, autoimmune diseases and/or severe primary or secondary immune deficiencies.
3. Patients receiving immunosuppressive therapy.
4. Patients receiving β -blockers (including topical formulations).
5. Associated diseases contraindicating the use of epinephrine: cardiovascular disease or severe hypertension.

Through a process of stratified randomization (according to sex), participants will be randomly assigned to one of 2 study groups. The first group will receive active desensitization, and the second group will not receive any treatment but will be followed up regularly (Appendix A Table 2). Desensitization will be offered to the observation groups following the trial, should the outcome be successful in the treatment group.

3.2 Oral challenge test to milk. Prior to initiating desensitization and following treatment, the subjects will undergo a placebo controlled oral challenge to milk. These challenges will determine the level at which the children react and will be the baseline to follow their improvement in oral tolerance following therapy.

Oral challenges will be single blinded and will be performed with fresh cow's milk, with increasing doses taken orally every 10 to 15 minutes up to a total of 150ml of milk (doses of 0.1, 0.3, 1.0, 3.0, 10.0, 30.0, 45ml, 60 mL) ^{(49,82) (83)}. Patients will receive 2 challenges per day, 1 placebo and 1 with the active substance (milk). Nurses in the Medical Day Unit/Center for Investigative Medicine will prepare the food and randomize the placebo challenges. Unless contraindicated, the placebo will be soy or rice-based milk. If the challenge is negative after 150 ml of milk, results will be confirmed by means of open challenge, using 250ml of yogurt or ice cream 1 hour after completion of the blinded portion(29) according to the recommendations of the European Academy of Allergology and Clinical Immunology (5). After completing the challenge, patients will be kept under observation for at least 2 hours. Only objective symptoms will be considered to be indicative of a positive allergic reaction (29). Food challenges will be scored as positive if a single symptom or any of the following objective clinical reactions will be observed: urticaria, angioedema, wheezing, rhinitis, vomiting, diarrhea, protracted abdominal pain, exacerbation of atopic dermatitis, or shock. A single episode of vomiting will not be considered as a positive reaction, while severe and repetitive vomiting will. If the challenge is **negative**, ie, the subject is asymptomatic, he/she will be excluded from the study. Based on our experience, approximately 80% of those subjects ages 6 or greater, with positive history and positive skin tests, approached will fail the oral challenge and thus be eligible.

3.3 Oral Immunotherapy to Cow's Milk Protein: The desensitization protocol will be performed at the Medical Day Unit / Center for Investigative Medicine, under the direct supervision of the medical and nursing staff, and with full cardiopulmonary resuscitation measures available for the treatment of possible allergic reactions that could occur during the procedure. Oral and intravenous doses of diphenhydramine and intramuscular epinephrine and IV corticosteroid will be at the bedside at all times(3).

The desensitization process is adapted from Martorelli 2011 al (26) (Appendix B). We have based our protocol on this study, as it was used for infant desensitization and was associated with high resolution of allergy and low incidence of side effects.

3.3.1 2 Day Initial Rush Desensitization: After placement of an intravenous catheter, the desensitization will begin with a first dose of 1ml of diluted milk (1/100). If tolerated, subjects will then receive approximately doubling doses every 60 minutes until they reach 8 ml of 1/100 dilution, or the highest tolerated dose without adverse reaction. Those who reach the 8 ml dose will be administered 1.6 ml of a 1/10 dilution of whole cow's milk. On the second day the dose of 1.6 ml of the 1/10 dilution is repeated, and then doubling doses every 60 minutes are administered till a dose of 12 ml 1/10 dilution of milk is reached. If 12 ml (1/10) is tolerated, the final dose on day 2 will be 2.5 ml undiluted milk.

The patients will not be admitted, but will remain under observation for 2 hours after the final dose each day, with the possibility for increasing this period if required. A full list of doses can be found in Appendix B.

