4.0. Statistical Considerations

A: Sample Size calculation: Given that previous studies have attributed at least 50% improvement in the ability to tolerate milk(24) with an α of 0.05 and a power (1- β) of 0.80, a sample of 42 cases and 42 controls will be recruited.

B: Statistical Analysis: Statistical analyses will be performed using paired t-tests. A p value of <0.05 will be considered significant. Descriptive statistics of the variables including means, standard deviations and frequencies were computed for all study variables. The concentrations of milk –specific IgE, IgG and IgA, the size of the skin tests , T reg and Breg expression at the different study time-points will be compared with their baseline values using the one-sample paired t-test and to the control using a 2 sample t-test .

Multiple regression models will be used to assess factors associated with response to desensitization, including baseline demographic characteristics; gender; age; baseline SPT and specific IgE, Treg and Breg numbers, and vitamin D level.

5. Ethical Considerations

In the consent form given at study enrolment, participants will be advised that they will be randomly assigned to either oral immunotherapy or observation for a one year period. Participants will also be advised that their data will be shared only among the OIT study team. Participants in the observation control group who will not receive OIT treatment, will be told that they may to undergo such therapy after a year of observation and a positive oral food challenge.

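### The plan does not commit to a one-year milk challenge for every control, so the primary outcome could be missing selectively in that arm; it also leaves open whether randomization follows a positive baseline challenge

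*Combined protocol and SAP*

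**What the plan says.** **Outcome.** Section 3.3.6 makes desensitization at one year the primary outcome, with success meaning that 200 ml of milk is tolerated.

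**When challenges happen.** Section 3.2: "Prior to initiating desensitization and following treatment, the subjects will undergo a placebo controlled oral challenge to milk". The Experimental Approach paragraph places the outcome challenges before OIT, at the maximum OIT dose and after a year of therapy.

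**What controls have.** Section 3.3.4 (Control Subjects): "They will have skin testing and blood testing as on routine follow-ups, but they will be required to fill out symptoms diaries". At the end, "oral desensitization will be offered to the control patients who had not spontaneously achieved tolerance"; how tolerance is established is not said. Section 5 tells controls that they may have OIT "after a year of observation and a positive oral food challenge". Section 3.1 and the Experimental Approach make that offer depend on OIT having succeeded.

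**Randomization and eligibility.** The inclusion criteria in section 3.1 are a suggestive history plus a positive skin test or specific IgE. Section 3.1 then continues: "Through a process of stratified randomization (according to sex), participants will be randomly assigned to one of 2 study groups". The challenge appears only in section 3.2, where, if it is negative and "the subject is asymptomatic, he/she will be excluded from the study". About 80% of children of 6 or older with a positive history and skin test who are "approached will fail the oral challenge and thus be eligible". Appendix C puts the challenge at Visit 2, after consent and before the rush visits. It follows the OIT path and has no entry for randomization.

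**The concern.** A randomized comparison needs the primary outcome measured in the same way in both arms. Here the OIT arm has challenges tied to its treatment, while a control's challenge depends on wanting OIT and on OIT being offered. Controls who ask for OIT are likely to be those who still react. Those who have become tolerant have little reason to ask. An analysis of challenged controls only would then tend to understate control success and overstate the benefit of OIT. Counting unchallenged controls as failures errs in the same direction, and counting them as successes errs in the other. If OIT is not offered, no control need be challenged at all.

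The baseline question is separate. If the entry challenge were given only to children about to start OIT, already tolerant children would be removed from one arm and kept in the other, which biases against OIT. If it were given to both arms after allocation, children would be excluded after randomization. If it comes before allocation for everyone, neither problem arises. The text does not say which applies.

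**Working it through.** **1. The plan's own figure.** Section 4.0 gives 42 per arm from α 0.05, power 0.80 and at least 50% improvement, with no control rate, SD, test or sidedness. An absolute 50-point difference gives 9 to 19 per arm. A standardized difference of 0.5 gives 63 per arm (two-sided). A relative change gives 42 only with unstated rates such as 0.60 vs 0.30. The figure can be neither confirmed nor refuted, and this point does not depend on it.

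**2. Is a control's one-year outcome guaranteed?**

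- Section 3.3.6 needs a result at 200 ml.
- Section 3.3.4 supplies skin tests, blood tests and diaries. None of these yields that result.
- Section 3.2 and the Experimental Approach tie challenges to treatment, which controls do not have.
- Section 5 supplies a challenge only on the way to OIT, and section 3.1 makes OIT conditional.

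So no passage requires a one-year challenge of a control who declines OIT, or of any control if OIT is not offered. The documents do not say how many this would be. With m unchallenged controls, the control success rate is known only to within m/42: 1/42 = 2.4 points each. As illustrations, m = 5 gives 11.9 points, m = 10 gives 23.8, and m = 42 gives no control outcome at all.

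**3. Baseline: size if only OIT children were challenged.** This scenario is not established by the text.

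- Share negative, from section 3.2: 1 − 0.80 = 0.20.
- Controls already tolerant: 42 × 0.20 = 8.4. The chance of at least one is 1 − 0.80^42 = 0.9999.
- OIT children remaining: 42 × 0.80 = 33.6, about 34.
- Observed control success: 0.20 + 0.80 × true control success. This assumes that tolerant children stay tolerant and that all controls are challenged at one year.

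Power = Φ((|p1 − p2| − 1.96·se0)/se1), with se0 = √(p̄(1 − p̄)(1/n1 + 1/n2)) and se1 = √(p1(1 − p1)/n1 + p2(1 − p2)/n2), two-sided 0.05. Success rates are assumptions, because the documents give none.

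| OIT success | True control | Observed control | Difference (points) | Power, 42 vs 42 undiluted | Power, 34 vs 42 diluted |
|---|---|---|---|---|---|
| 50% | 0% | 20% | 50 → 30 | >99% | 79% |
| 50% | 5% | 24% | 45 → 26 | >99% | 66% |
| 50% | 10% | 28% | 40 → 22 | 99% | 50% |
| 70% | 0% | 20% | 70 → 50 | >99% | >99% |
| 70% | 5% | 24% | 65 → 46 | >99% | 99% |
| 70% | 10% | 28% | 60 → 42 | >99% | 97% |

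First row in full: p̄ = (42 × 0.20 + 34 × 0.50)/76 = 0.334; se0 = 0.109; se1 = 0.106; (0.30 − 1.96 × 0.1088)/0.1057 = 0.82; Φ(0.82) = 0.79.

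**4. Baseline: the two other readings.** If both arms were challenged after allocation and negatives dropped, about 34 per arm would remain. With OIT success of 50% and control success of 0 to 10%, power is still about 97% or more, so the harm is mainly loss of the randomized set. If everyone is challenged before allocation, about 84/0.80 = 105 children are challenged to randomize 84, and there is no bias.

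**The case against.** The baseline text leans towards a screen of everyone. Section 3.2 speaks of the subjects without naming an arm. A negative result excludes from the study, not from an arm. The 80% is a yield among children approached, who thereby become eligible, and Appendix C has the challenge straight after consent. A reader might infer from the order of sections 3.1 and 3.2 that children are randomized first, so that tolerant children stay among the controls or are dropped after allocation. The documents do not support that: order of description is not order of conduct, and no passage puts randomization before the challenge. This part of the objection stands, and the baseline point is therefore a request for clarity. It does not close the question, because the inclusion criteria omit the challenge and the schedule omits randomization.

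On the one-year outcome, section 5 does name a control challenge, and section 3.3.4 presupposes that someone establishes which controls became tolerant. So it would be wrong to say that controls are never challenged. But the first is a condition for crossing over and the second names no method, so neither commits to a challenge of every control.

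Section 3.1 refers control follow-up to Appendix A Table 2. That table is not in the text available for this review and might list a control challenge.

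**Conclusion.** The one-year point holds. As written, the primary outcome is secured for controls only if they go on to seek OIT and it is offered, so it can be missing in a way related to the outcome itself. The size cannot be computed from the documents; it is 2.4 points of uncertainty in the control rate per unchallenged control. The likely direction, overstating OIT when only challenged controls are analysed, rests on the assumption that children who still react are the ones who seek OIT.

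The baseline point holds only as an ambiguity. On its worst reading about 8 of 42 controls would be tolerant at entry and the treatment difference would shrink in every assumed case. Power would be about 79% to 50% with OIT success of 50% and true control success of 0 to 10%, and about 97% or more with OIT success of 70%. A reader might take these figures as the expected loss of power. They are conditional on a reading that the text does not favour and on assumed success rates.

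Both parts are subject to Appendix A Table 2.

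**What to change.** - In section 3.1, state that every child completes the oral challenge and that only those with a positive result are randomized. Add the positive challenge to the inclusion criteria.
- In Appendix C, place randomization after Visit 2 and add a control-arm schedule.
- In sections 3.2 and 3.3.4, require the same 12-month challenge in both arms, whether or not the child wants OIT and before any decision to offer it.
- When specifying that challenge, reconcile its volume with the outcome: section 3.2 stops at 150 ml in total, section 3.3.3 names 300 ml, and success is defined at 200 ml.

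**Cost.** If a screen of all children was always intended, the baseline change is wording only, and the number challenged at entry is unchanged. Controls who would not otherwise have been challenged have one or two extra challenge days, with the burden and reaction risk that a challenge carries. Controls who cross over already need a challenge. Section 3.3.3 spells out a 12-month challenge only for OIT children below 200 ml, so some OIT children may also need one, unless the year-end challenge in the Experimental Approach already covers them.
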